Adverse events and serious adverse events will be collected under this extension study protocol from the administration of the first dose of extension study drug until the Safety Follow-up visit approximately 30 days after the last dose of study drug or the date of initiation of another investigational agent or hormonal therapy affecting the hypothalamic-pituitary-gonadal axis or surgical intervention for uterine fibroids, whichever occurs first, as also specified in the study Schedule of Activities (Table 1-1). Serious adverse events reported to the investigator after the safety reporting period should be reported to the sponsor if the investigator assesses the event as related to the study drug treatment.

Reporting instructions for serious adverse events are provided in Section 7.6.

7.3. **Assigning Causal Relationship to Study Drug**

The reasonable possibility of the relationship of an adverse event to study drug(s) is to be assessed with careful medical consideration at the time of evaluation of an adverse event. The following definitions are to be used for the relationship of the adverse event to study drug:

- **Probably related**: A clinical event, including laboratory test abnormality, with a reasonable time sequence to administration of the drug, unlikely attributed to concurrent disease or other drugs or chemicals, and that follows a clinically reasonable response on readministration (rechallenge) or withdrawal (dechallenge).
- Possibly related: A clinical event, including laboratory test abnormality, with a reasonable time sequence to administration of the drug but that could also be explained by concurrent disease or other drugs or chemicals. Information on drug withdrawal may be lacking or unclear.
- Not related: A clinical event, including laboratory test abnormality, with a temporal relationship to drug administration that makes a causal relationship improbable and/or in which other drugs, chemicals, or underlying disease provide a plausible explanation.

All adverse events, whether related to study drug, must be fully and completely documented on the adverse event page of the eCRF and in the patient's clinical record. In the event a patient is withdrawn from the study because of an adverse event, it must be recorded on the eCRF as such.

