4.6. Contraception/Pregnancy Avoidance

In this study, medications and devices containing hormones for contraception are excluded. Patients must agree to use nonhormonal contraception throughout the study unless any of the following apply:

- Has a sexual partner(s) who was vasectomized at least 6 months prior to the Week 52/Baseline visit;
- Had a bilateral tubal occlusion (including ligation and blockage methods such as EssureTM) at least 4 months prior to the Week 52/Baseline visit (patients with Essure must have prior confirmation of tubal occlusion by hysterosalpingogram) and there must be no evidence of post-Essure syndrome;
- Has a nonhormonal intrauterine device (e.g., Paragard®) placed in the uterus;
- Is not sexually active with men; periodic sexual relationship(s) with men requires the use of nonhormonal contraception as described below;
- Practices total abstinence from sexual intercourse, as her preferred lifestyle; periodic abstinence is not acceptable.

The only acceptable methods of contraception for whom none of the above methods apply are:

- Condom (male or female condom) with or without spermicide (cream, spray, foam, gel, suppository, or polymer film);
- Diaphragm with spermicide (condom may or may not be used);
- Cervical cap with spermicide (condom may or may not be used); or
- Vaginal sponge impregnated with spermicide used with a condom.

Patients will be provided with information on acceptable methods of contraception as part of the informed consent process and will confirm with signing of the consent form that they understand the requirements for avoidance of pregnancy during the course of the study. Patients may not donate ova during the course of the study and for 2 months following the last dose of study drug.

A patient may start hormonal contraception 4 weeks after her last study dose of study drug provided her menstrual cycle has returned.

Urine pregnancy tests will be performed at monthly intervals during the study (including prior to receiving the first dose of study drug), and patients will receive continued guidance with respect to the avoidance of pregnancy as part of the study procedures. Patients who become pregnant during the study will be withdrawn from the study and followed for pregnancy outcome (see Section 7.8).

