5.9.3. Prohibited Non-Drug Therapies

Surgical and other interventional treatment of uterine fibroids is prohibited from the Week 52/Baseline visit until the patient's final study visit unless urgently needed for patient safety.

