7.1.2. Serious Adverse Event

A serious adverse event is any untoward medical occurrence that, at any dose:

- a. Results in death;
- b. Is life-threatening;

NOTE: The term "life-threatening" in the definition of "serious" refers to an event in which the study participant was at risk of death at the time of the event. It does not refer to an event which hypothetically might have caused death if it were more severe. For example, druginduced hepatitis that resolved without evidence of hepatic failure would not be considered life-threatening even though drug-induced hepatitis can be fatal.

c. Requires hospitalization or prolongation of existing hospitalization;

NOTE: In general, hospitalization signifies that the patient has been admitted to a hospital, independent of the duration of that hospitalization. Complications that occur during hospitalization are adverse events. If a complication prolongs hospitalization or fulfills any other serious criteria, the event is serious. When in doubt as to whether "hospitalization" occurred or was necessary, the adverse event should be considered serious. Hospitalization

for elective treatment of a pre-existing condition that did not worsen from the Week 52/Baseline visit is not considered an adverse event.

d. Results in persistent or significant disability/incapacity;

NOTE: The term disability means a substantial disruption of a person's ability to conduct normal life functions. This definition is not intended to include experiences of relatively minor medical significance such as uncomplicated headache, nausea, vomiting, diarrhea, influenza, and accidental trauma (e.g., sprained ankle), which may interfere or prevent everyday life functions but do not constitute a substantial disruption.

- e. Is a congenital anomaly/birth defect;
- f. Important medical events that jeopardize the patient and may require medical or surgical intervention to prevent one of the outcomes listed above. Examples of such events are invasive or malignant cancers, intensive treatment in an emergency room or at home for allergic bronchospasm, blood dyscrasias or convulsions that do not result in hospitalization, or development of drug dependency or drug abuse.

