Overdose and pregnancy in the patient will be reported as described in Section 7.7 and Section 7.8, respectively.

7.2.1. **Adverse Event Reporting Period**

Adverse events and serious adverse events will be collected under this extension study protocol from the administration of the first dose of extension study drug until the Safety Follow-up visit approximately 30 days after the last dose of study drug or the date of initiation of another investigational agent or hormonal therapy affecting the hypothalamic-pituitary-gonadal axis or surgical intervention for uterine fibroids, whichever occurs first, as also specified in the study Schedule of Activities (Table 1-1). Serious adverse events reported to the investigator after the safety reporting period should be reported to the sponsor if the investigator assesses the event as related to the study drug treatment.

Reporting instructions for serious adverse events are provided in Section 7.6.

7.3. **Assigning Causal Relationship to Study Drug**

The reasonable possibility of the relationship of an adverse event to study drug(s) is to be assessed with careful medical consideration at the time of evaluation of an adverse event. The following definitions are to be used for the relationship of the adverse event to study drug:

- **Probably related**: A clinical event, including laboratory test abnormality, with a reasonable time sequence to administration of the drug, unlikely attributed to concurrent disease or other drugs or chemicals, and that follows a clinically reasonable response on readministration (rechallenge) or withdrawal (dechallenge).
- Possibly related: A clinical event, including laboratory test abnormality, with a reasonable time sequence to administration of the drug but that could also be explained by concurrent disease or other drugs or chemicals. Information on drug withdrawal may be lacking or unclear.
- Not related: A clinical event, including laboratory test abnormality, with a temporal relationship to drug administration that makes a causal relationship improbable and/or in which other drugs, chemicals, or underlying disease provide a plausible explanation.

All adverse events, whether related to study drug, must be fully and completely documented on the adverse event page of the eCRF and in the patient's clinical record. In the event a patient is withdrawn from the study because of an adverse event, it must be recorded on the eCRF as such.

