9.5. Safety Analyses

Safety assessments will include treatment-emergent adverse events, vital signs, physical examinations, clinical laboratory tests, 12-lead ECGs, and results of measurements of bone mineral density by DXA.

The treatment-emergent period will be defined as the period of time from the first dose date of extension study drug through approximately 30 days after the last dose of study drug, or the date of initiation of another investigational agent or hormonal therapy affecting the hypothalamic-pituitary-gonadal axis or surgical intervention for uterine fibroids, whichever occurs first. Safety will be assessed through summaries of adverse events, the frequency of treatment discontinuations due to adverse events, laboratory evaluations, and bone densitometry results.

The severity of all adverse events is to be evaluated by the investigator based on the National Cancer Institute's CTCAE. All adverse events will be coded to preferred term and system organ class using MedDRA 20.0 or higher. The incidence of adverse events will be presented by MedDRA system organ class and preferred term, relationship to study drug treatment, and severity. A patient reporting the same adverse event more than once is counted once, and at the maximum severity or strongest relationship to study drug treatment when calculating incidence.

Laboratory data consist of chemistry, hematology, and hormonal tests. Only data collected by the central laboratory will be used to do the analyses. The National Cancer Institute CTCAE, will be used to categorize toxicity grade for the laboratory parameters. Shift tables will be provided for each gradable parameter to summarize baseline toxicity grade versus post-baseline toxicity grade. For laboratory parameters that are not gradable by the CTCAE, a shift table based upon the normal range (low, normal, and high) will be provided for each parameter to summarize the study Baseline versus post-baseline results. All data will be listed and summarized by visit. The change from study Baseline to each post-baseline study visit will be presented by study treatment group for each laboratory test.

For vital signs parameters, including temperature, all data will be listed and summarized by visit. The change from study Baseline to each post-baseline study visit will be presented by study treatment group for each parameter.

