9.1. Adverse Events

Adverse events will be collected from the time of the first dose of randomized withdrawal study drug through the safety follow up visit approximately 30 days after the last dose of randomized withdrawal study drug (if no retreatment was initiated) or approximately 30 days after the last dose of retreatment drug (if the retreatment was initiated), or the date of initiation of another investigational agent or hormonal therapy (eg, elagolix, acotol) or surgical intervention (eg, uterine artery embolization), whichever occurs first. Serious adverse events reported to the investigator after the safety reporting period should be reported to the sponsor if the investigator assesses the event as related to study drug.

The severity of all treatment-emergent adverse events will be evaluated by the investigator based on the National Cancer Institute's Common Terminology Criteria for Adverse Events (CTCAE), v.5.0 dated 27 Nov 2017, and will be coded to preferred term and system organ class using MedDRA 24.0 or higher.

A treatment-emergent adverse event for cumulative treatment period (including the randomized treatment and the retreatment periods) is defined as any adverse event that onsets or worsens after administration of the first dose of randomized withdrawal study drug.

For patients who stayed on the randomized treatment till end of the study, a treatment-emergent adverse event for the randomized treatment period is defined as any adverse event that onsets or worsens after administration of the first dose of randomized withdrawal study drug. For patients who had the retreatment drug initiated, any adverse event that onsets or worsens after administration of the first dose of randomized withdrawal study drug and prior to the initiation of the retreatment drug is defined as treatment-emergent adverse event for the randomized treatment period.

For patients who started the retreatment drug, a treatment-emergent adverse event for the retreatment period is defined as any adverse event that onsets after the initiation of retreatment drug.

Adverse event summaries will be based on treatment-emergent adverse events in the randomized withdrawal study, unless otherwise specified. The summaries will mainly be done for the cumulative treatment period. Some selected summaries may be provided for the randomized withdraw period and the retreatment period separately. All adverse events will be listed in by-patient listings.

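### Adverse event collection closes at fibroid surgery or another hormonal or investigational therapy even if study drug continues, in conflict with Table 1-1 and the SAP's treatment-emergent definition

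*Protocol*

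**What the plan says.** Protocol 7.2.1 collects AEs and SAEs up to the Safety Follow-up visit, about 30 days after last dose. Collection stops sooner if another investigational agent is started, and the list of early stops goes on with "hormonal therapy affecting the hypothalamic-pituitary-gonadal axis or surgical intervention for uterine fibroids, whichever occurs first". The wording is the same in the 11 July 2018 protocol and in Amendment 1. The section adds that the limit also appears in Table 1-1, and that SAEs reported after the window still go to the sponsor if the investigator judges them related to study drug.

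Protocol 9.5 applies the same limit to analysis. It begins: "The treatment-emergent period will be defined as the period of time from the first dose date of extension study drug through approximately 30 days". Those days are counted from last dose, and the same early-ending events close the period if they come sooner. The collection sentence in SAP 9.1 also stops at another agent, hormonal therapy "or surgical intervention (eg, uterine artery embolization), whichever occurs first".

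The surrounding rules are these:

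- Protocol 5.9.3 bars fibroid surgery until the "final study visit unless urgently needed for patient safety".
- Protocol 5.9.1 prohibits hormonal drug classes through Safety Follow-up. SAP 5.2 lists receipt of a prohibited medication among important deviations.
- The list of reasons for removal from therapy in Protocol 4.5 names neither fibroid surgery nor prohibited hormone use.
- Table 1-1 marks AE collection at every visit and has no footnote that cuts it short.
- Protocol 6.3 places the follow-up visit about 30 days after last dose, or before the new therapy or surgery if that comes first.

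**The concern.** A safety window may reasonably close when another treatment takes over after study drug has ended. Here the closing event is not tied to the end of study drug. A woman can have urgent surgery, or take a prohibited hormone, and continue randomized or open-label treatment. She still attends visits every four weeks, but the stated collection period is over.

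What is at stake is the completeness of on-drug safety data, in a study whose stated objectives include safety for up to a further 52 weeks. There is also a practical problem. A site that follows Table 1-1 keeps recording events, while a site that follows section 7.2.1 stops. A programmer who follows Protocol 9.5 drops later events from the treatment-emergent tables, while one who follows SAP 9.1 keeps them.

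**Working it through.** The plan states no figure to reproduce. The check is to set the rules side by side and see what the literal rule leaves out.

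**1. The rules compared**

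| Source | What it governs | Closes at surgery or other therapy? | Requires study drug to have stopped? |
|---|---|---|---|
| Protocol 7.2.1 | AE and SAE collection | Yes | No |
| Protocol 9.5 | Treatment-emergent period | Yes | No |
| SAP 9.1, collection sentence | AE collection | Yes | No |
| SAP 9.1, cumulative treatment-emergent definition | Counting | No; no end date given | Not applicable |
| SAP 4.4.2, partial dates | Counting | Uses an end date of the treatment-emergent period that the SAP does not define | Not applicable |
| Protocol Table 1-1 | AE collection by visit | No | Not applicable |

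The SAP's open-ended definition counts whatever has been recorded. It cannot restore events that were never collected.

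**2. The literal window**

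Let L be the last-dose day, H the first day of another hormonal or investigational therapy, and S the day of fibroid surgery. The window closes at min(L + 30, H, S). If H or S is earlier than L, it closes on drug.

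**3. What is then not collected**

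Related SAEs stay reportable under 7.2.1. SAP 9.1.3 includes deaths on study and in post-treatment follow-up. The remainder is non-serious AEs and SAEs judged unrelated.

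**4. Illustration for one woman**

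The target days come from SAP Table 2: Week 60 is Day 57, Week 76 is Day 169 and Week 104 is Day 365. The planned window is 365 + 30 = 395 days.

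- Surgery at Week 60, drug continued to Week 104: 395 − 57 = 338 days outside the window (338/395 = 85.6%). Of these, 365 − 57 = 308 are on drug and 30 are follow-up.
- Surgery at Week 76, drug continued to Week 104: 395 − 169 = 226 days outside the window (226/395 = 57.2%). Of these, 365 − 169 = 196 are on drug and 30 are follow-up.

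**5. Scale across the trial, by assumption only**

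The documents give no rate of on-study surgery or added hormones. If 1% to 3% of 360 women were affected, that is 3.6 to 10.8, or about 4 to 11 women. If all had the event at Week 60 and stayed on drug, the days outside the window would be 4 × 338 = 1,352 to 11 × 338 = 3,718. The planned total is 360 × 395 = 142,200 days, so the share is about 1.0% to 2.6%. Later events, or drug stopped early, would lower it.

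**The case against.** The strongest defence is that the cut-off is a deliberate choice about attribution. Once a woman has surgery or another hormone, events are hard to assign to study drug. SAP 4.3.7 restricts bone density and safety follow-up assessments at the same events, and Protocol 6.3 moves the follow-up visit ahead of them. The plan thus treats these events as the end of participation. Expected surgery bars entry, on-study surgery must be urgent, hormones are prohibited, and the gross-noncompliance item in 4.5 lets an investigator remove a woman who takes them. This stands as a reason to expect few cases. It does not supply the missing condition that study drug has stopped, and confounding can be handled by flagging events instead of not collecting them.

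Several stronger readings are tempting but not supported:

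- *SAE collection ends outright and on-drug events are lost.* Related SAEs remain reportable and deaths are analysed. Protocol 7.2 also has existing events followed until they resolve, stabilize or become chronic.
- *Later events cannot be treatment-emergent.* That follows from Protocol 9.5 only. The SAP definition has no end date, and SAP 4.4.2 counts doubtful partial dates as treatment-emergent.
- *Surgery always permits a verdict of not related.* That category in 7.3 refers to a temporal relationship that makes causality improbable, or one "in which other drugs, chemicals, or underlying disease provide a plausible explanation"; surgery is not named. The adjacent category, possibly related, covers events with a reasonable time sequence and another explanation, and SAP 9.1.1 counts it as related. The two categories overlap, so the route is discretionary but not closed.
- *Section 7.1.2 contradicts the window.* It says "Complications that occur during hospitalization are adverse events", but it defines seriousness and sets no collection period.
- *The loss must differ between arms.* The planning rates (40% responders on placebo, 60% on active) imply more returning bleeding on placebo. However, the planned response is open-label retreatment, and the documents give no surgery rate by arm.
- *Permitted contraception cuts follow-up materially.* Protocol 4.6 says "A patient may start hormonal contraception 4 weeks after her last study dose of study drug provided her menstrual cycle has returned". Day 28 falls inside the follow-up visit window (30 − 3 = 27 to 30 + 18 = 48 days). The nominal loss is 30 − 28 = 2 days, off drug, and 6.3 puts the visit before the therapy starts.

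**Conclusion.** The point holds as a gap and an inconsistency in wording. As written, Protocol 7.2.1, Protocol 9.5 and the SAP 9.1 collection sentence can close the window while a woman is on randomized or open-label drug. The exposed data are non-serious AEs and SAEs judged unrelated. The documents also disagree with each other: Table 1-1 keeps collecting, and the SAP counts without an end date.

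The likely size is small. The conclusion rests on a literal reading of the closing rule and on a woman continuing drug after surgery or a prohibited hormone, which the documents allow but do not describe as usual. The 86% and 57% figures are single-patient illustrations and the 1% to 3% rate is an assumption; neither should be read as expected loss for the trial. Some sites may in practice follow Table 1-1 and lose nothing.

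A reader might go further and ask that collection always run to 30 days after last dose, whatever therapy starts after study drug has ended. That is more debatable, because those events are off drug and confounded, and the follow-up visit in 6.3 would also have to move. This point does not depend on it. It also takes no position on whether a woman should continue study drug after surgery or another hormone.

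**What to change.** In Protocol 7.2.1 and 9.5 and SAP 9.1, state that the early cut-off applies only after the last dose of randomized or open-label study drug. Surgery or another therapy dated on or before the last dose would not close the window; one dated after it would, as now. All AEs and SAEs with onset on drug are then collected and counted as treatment-emergent.

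Alongside this:

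- Record the date of the surgery or other therapy, flag events with onset on or after it, and repeat the AE overview without the flagged events.
- Give the SAP treatment-emergent period the same end date as the revised Protocol 9.5, so that the partial-date rule in SAP 4.4.2 has an end date to refer to.
- Reconcile Table 1-1 and Protocol 6.3 with the rule, including when the follow-up visit falls if surgery or other therapy occurs on drug.

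The cost is protocol and SAP wording, one flag and one repeated summary. On-drug collection uses visits already in Table 1-1. The downside is that some events caused by the other therapy enter the main tables; the repeated overview shows how much they matter.
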